7.4 Criteria and Procedure for Stopping the Trial/Treatment

1. The patient or their representative requests to withdraw from the clinical trial;
2. The subject fails to follow the requirements of the standard operating protocol of the trial and seriously violates the protocol so that the data of this subject are unreliable.
3. An AE or SAE occurs, rendering the patient unfit to continue in this clinical trial.
4. Lost to follow-up;
5. Those who, in the investigator's opinion, are unfit to continue participating in this clinical trial.

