3.1 Purpose of the Clinical Trial

Through this real-world study, to analyze the response of functional constipation patients with different severity, treatment status, capsule dosage, and combined medication to Vibrabot capsule, as well as the duration of efficacy maintenance during the follow-up period; to compare the efficacy with patients treated with drugs or other therapies during the same period, explore the possibility of curing functional constipation patients, further improve the treatment satisfaction of constipation patients, and promote the establishment and application of consensus or guidelines for the use of Vibrabot capsule in treating functional constipation.

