7.1.2 Visit Content

Each patient will undergo a series of study visits, including screening, treatment visit, and follow-up visit. The visit process is briefly described as follows:

Visit 1 (0 ~ 1 day) - Baseline/Screening Period:

This visit includes:

The patient will sign an informed consent form;

Set the inclusion/exclusion criteria;

Guide patients to fill out the questionnaire using the Official Account and complete the *Baseline Period Questionnaire* in the Official Account.

Prescription Vibrabot capsule treatment or other treatment options.

Visit 2 (Week 2 ±3 days) - Treatment Period 1:

This visit includes:

Fill out the *Daily Bowel Movement Questionnaire* in the WeChat Official Account every day, take Vibrabot capsules on time or opt for other treatment plans;

Fill out the *Constipation Symptom Self-Assessment Scale and Assessment Scale for Quality of Life with Constipation* in the Official Account every 2 treatment weeks.

Record adverse events and concomitant treatments;

Prescription Vibrabot capsules or other treatment options.

Visit 3 (Week 4±3 days) - Treatment Period 2

This visit includes:

Fill out the *Daily Bowel Movement Questionnaire* in the WeChat Official Account every day, take Vibrabot capsules on time or opt for other treatment plans;

Fill out the *Constipation Symptom Self-Assessment Scale and Assessment Scale for Quality of Life with Constipation* in the Official Account every 2 treatment weeks.

Record adverse events and concomitant treatments;

Prescription Vibrabot capsules or other treatment options.

Visit 4 (Week 6 ±3 days) - Treatment Period 3

This visit includes:

Fill out the *Daily Bowel Movement Questionnaire* in the WeChat Official Account every day, take Vibrabot capsules on time or opt for other treatment plans;

Fill out the *Constipation Symptom Self-Assessment Scale and Assessment Scale for Quality of Life with Constipation* in the Official Account every 2 treatment weeks.

Record adverse events and concomitant treatments.

Visit 5 (Week 10±3 days) - Follow-up Period:

This visit includes:

Fill out the *Daily Bowel Movement Questionnaire* in the WeChat Official Account every day;

Fill out the *Constipation Symptom Self-Assessment Scale and Assessment Scale for Quality of Life with Constipation* in the Official Account every 2 treatment weeks;

Record adverse events and concomitant treatments.

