7.2 Secondary Efficacy Endpoints

- 1) Proportion of constipated patients who use/do not use other constipation treatment methods during treatment and after the vibrating capsule treatment and at the end of follow-up;
- 2) Proportion of patients with an average increase of ≥ 1 CSBMs per week compared to the baseline period;
- 3) Proportion of respondents with an average of ≥ 3 SBMs per week during the treatment period;
- 4) Proportion of subjects with ≥ 3 SBMs per week and an increase of ≥ 1 CSBMs during at least 4 weeks of treatment compared to baseline;
- 5) Proportion of patients with an average increase of ≥ 1 CSBMs per week during the follow-up phase compared to the baseline period;
- 6) Proportion of patients with an average of ≥ 3 SBMs per week during the follow-up phase;
- 7) Proportion of patients with a reduction of ≥ 1 point in total PAC-QOL and PAC-SYM scores after treatment compared to the baseline period;
- 8) Proportion of patients with a reduction of ≥ 1 point in total PAC-QOL and PAC-SYM scores after follow-up compared to the baseline period;
- 9) Time of first use of laxative or enema after a course of vibrating capsule treatment (6 weeks);
- 10) Proportion of constipated patients (including different constipation types, occupations, age groups, BMI, gender, and baseline treatment status) responding to vibrating capsule treatment and at the end of follow-up.

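### Section 7.4 words AE/SAE and investigator-judgement stops as leaving the trial, so the unimputed follow-up endpoints 5, 6 and 8 may lose those patients

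*Combined protocol and SAP*

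**What the plan says.** Section 7.4 of the combined protocol and SAP is headed "Criteria and Procedure for Stopping the Trial/Treatment". Under that heading is one list of five items, with nothing to show which end treatment only and which end participation.

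- Item 3: "An AE or SAE occurs, rendering the patient unfit to continue in this clinical trial".
- Item 5: those who, in the investigator's view, "are unfit to continue participating in this clinical trial".
- Item 2: a patient who "seriously violates the protocol so that the data of this subject are unreliable".
- Items 1 and 4: withdrawal at the patient's request, and loss to follow-up.

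The other relevant provisions are these.

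- **Schedule (7.1.2).** Every patient is to have screening, treatment and follow-up visits. At Visits 2 to 4 patients fill in the daily diary and "take Vibrabot capsules on time or opt for other treatment plans". "Visit 5 (Week 10±3 days) - Follow-up Period" again calls for the diary, both scales, and AE and concomitant-treatment recording.
- **Purpose (3.1).** The aims include the response to the capsule "as well as the duration of efficacy maintenance during the follow-up period".
- **Endpoints (7.2, secondary).** Endpoint 5 concerns the increase in "CSBMs per week during the follow-up phase compared to the baseline period". Endpoint 6 concerns SBM frequency in the same phase. Endpoint 8 concerns PAC-QOL and PAC-SYM after follow-up.
- **Analysis (8.1, 8.3).** The FAS keeps anyone with a baseline evaluation and at least one treatment. Missing secondary data are not imputed, and 8.3 says in general that missing data are not filled in.
- **After an AE (13.1.3).** The AE itself is followed until it is stable or gone. Efficacy data are not mentioned.

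**The concern.** Stopping a treatment and leaving a study are different events, and 7.4 does not separate them. Applied as worded, items 3 and 5 take the patient out of the study. Nothing elsewhere says that such a patient still completes the questionnaires at Weeks 6 and 10.

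Removal for an adverse event, or because the investigator judges the patient unfit, may be related to how the patient is doing. The follow-up endpoints describe how long benefit lasts, which is a stated purpose of the study. If the removed patients differ in response from those who stay, the reported follow-up proportions do not describe the FAS. Data not collected at Week 10 cannot be recovered at analysis. With nine sites, the combined list may also be applied differently from one site to the next.

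**Working it through.** **The plan's nearest figure.** The plan gives no stopping rate. It does give a 20% allowance for loss to follow-up (8.1). Using the plan's inputs (null 0.40, expected 0.50, power 0.80) and two-sided alpha 0.05:

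n = [1.960 × √(0.40 × 0.60) + 0.842 × √(0.50 × 0.50)]² / 0.10² = 190.7, rounded up to 191; then 191 / 0.80 = 238.75, rounded up to 239.

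Both stated figures reproduce. The allowance protects the number of evaluable patients. It does not correct a proportion when the missing patients differ from the rest.

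**Inputs for the illustration.**
- Planned capsule patients: 300 (8.1).
- True follow-up response p = 0.50: an assumption. The plan gives no follow-up rate, and 50% is its expected treatment response.
- Share removed s = 1%, 2%, 5% or 10% (3, 6, 15 or 30 patients): an assumption.
- Response among those removed r = 20%, 35% or 50%: an assumption.

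**Formulas.** The plan does not state the denominator for these endpoints, so both are shown.
- Observed patients only: (p − s·r) / (1 − s); bias = s(p − r) / (1 − s).
- All FAS patients, with the unobserved not counted as responders: p − s·r; bias = −s·r.

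Worked case, s = 0.10 and r = 0.20: observed only (0.50 − 0.02) / 0.90 = 0.533; all FAS 0.50 − 0.02 = 0.48.

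| Removed | r | Observed-only rate | Bias (points) | All-FAS rate | Bias (points) |
|---|---|---|---|---|---|
| 1% | 20% | 50.3% | +0.3 | 49.8% | −0.2 |
| 2% | 20% | 50.6% | +0.6 | 49.6% | −0.4 |
| 5% | 20% | 51.6% | +1.6 | 49.0% | −1.0 |
| 10% | 20% | 53.3% | +3.3 | 48.0% | −2.0 |
| 5% | 35% | 50.8% | +0.8 | 48.25% | −1.75 |
| 10% | 35% | 51.7% | +1.7 | 46.5% | −3.5 |
| 10% | 50% | 50.0% | 0 | 45.0% | −5.0 |

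**Scale.** The 95% half-width for 50% of 300 is 1.96 × √(0.25 / 300) = 5.7 points. The largest observed-only bias shown is 3.33 / 5.66 = 0.59 of that. At 1% to 2% removed, the bias is well under one point on either denominator in the 20% rows.

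The two denominators move the rate in opposite directions. If the removed patients respond like the rest, the observed-only rate is unbiased and the all-FAS rate is still too low.

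**The case against.** The strongest reply is that the schedule already covers people who stop the capsule. Section 7.1.2 gives every patient a follow-up visit and lets patients change to other treatment while completing the same diary. Section 13.1.1 mentions discontinuing the device for a severe AE without mentioning trial exit. This stands. A reader might infer from 7.4 that everyone who discontinues is dropped from follow-up or from the analysis. The documents do not support that: the gap is limited to patients judged unfit for the study itself under items 3 and 5, and even they remain in the FAS.

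A reader might also count item 2. That item applies only where the data are already called unreliable, so more self-reported diary entries would add little, and the PPS definition already excludes protocol violators. Item 2 is left out of the point.

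A third reply is that Week 10 data from someone who never completed the course may not measure maintenance of effect. That is arguable, and endpoint 9 is tied to a 6-week course. Endpoints 5, 6 and 8 carry no such condition, and the FAS is said to follow the intention-to-treat principle as closely as possible, so collecting the data fits the plan's own stated aim.

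The last reply is size. Section 9.2 calls the risk relatively low and puts retention with capsule devices at about 0.73%, which is 0.0073 × 300, or about 2 patients. That is not a removal rate, but it gives no reason to expect a high one. This stands too, and it limits the weight of the point.

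**Conclusion.** The point holds in a limited form. Items 3 and 5 of 7.4 are worded as trial exit, no provision keeps those patients on the Week 6 and Week 10 questionnaires, and endpoints 5, 6 and 8 are not imputed. Those endpoints can therefore lose patients for reasons related to outcome.

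A reader might conclude that the reported follow-up rates will be too high. The documents do not establish that. Upward bias needs both an observed-only denominator, which the plan does not state, and poorer response among those removed. With all FAS patients as denominator the error runs the other way.

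Nor is the sample size affected: it rests on the primary endpoint, for which 8.1 provides imputation in the FAS and a 20% loss allowance. The point concerns secondary endpoints only.

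The size cannot be taken from the documents and is probably small. Every figure in the table rests on the assumed 50% true rate and on assumed removal and response rates. This is a cheap improvement in wording and data collection; it does not threaten the study's main result.

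**What to change.** Amend 7.4 as follows.

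1. An AE, SAE or investigator judgement stops the capsule or other treatment only. The patient stays in the FAS and continues the existing WeChat diary, both scales, and AE and concomitant-treatment recording to Weeks 6 and 10.
2. Data collection ends only if consent is withdrawn, the patient is lost, or the investigator documents a specific reason why completing questionnaires is itself inappropriate. This exception must be narrower than the present item 5, or nothing changes.
3. Serious violations (item 2) are left to the existing PPS exclusion.
4. The number removed under each 7.4 item, and the denominator used, are reported beside endpoints 5, 6 and 8.

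The cost is one wording amendment with EC approval, as 12.1.2 and 14 require. No visit or instrument is added. Off-treatment diaries will be less complete than on-treatment ones, and if an observed-only denominator is used the reported follow-up rates may be slightly lower.

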7.5 Expected Overall Duration of Clinical Trial and Reasons for Determination

The overall duration of the clinical trial includes the signing of the clinical trial protocol for all participating hospitals, ethical review meetings and post-meeting correction as per comments, trial initiation, patient enrollment and follow-up time, as well as the collection, statistics, and summary report writing time for trial data. It is expected to be from September 2023 to October 2025.

Reason: The estimated overall duration of this trial is approximately 2 years, based on the number of outpatient visits required for the application of test products in each hospital, the scheduling of patient follow-up times, and the process systems of various hospitals.

8. Statistical Considerations

8.1 Statistical Analysis of the Population

Sample Size Calculation

H0: The effectiveness rate of vibrating capsule treatment for constipation $\leq 50\%$

H1: The effectiveness rate of vibrating capsule treatment for constipation $> 50\%$

In a single-group design, if the study goal is to evaluate the effectiveness of vibrating capsule

treatment for constipation and compare it with the expected 50% effectiveness rate, then a one-sample proportion test can be considered for sample size calculation.

Sample size calculation formula for single sample proportion test is:

$$n = \frac{\left[Z_{1-\alpha} \sqrt{P_0(1-P_0)} + Z_{\beta} \sqrt{P_T(1-P_T)} \right]^2}{(P_T - P_0)^2}$$

Where:

- (1) p is the overall expected success rate (here it is estimated that the effectiveness of treating constipation with vibrating capsules is 50%);
- (2) p_0 is the success rate under the null hypothesis (assuming a 40% success rate under the null hypothesis);
- (3) The probability of Type I error α is set to 0.05, and the probability of Type II error β is set to 0.2 (i.e., the statistical power is $1-\beta=0.8$);

At least 191 participants are needed for this study. Assuming a 20% loss to follow-up, the final sample size required is 239. Considering this is a real-world study and taking into account the outpatient volume of the participating center, it is planned to enroll 300 patients who will take vibrating capsules for 6 weeks, and at the same time, include ≥ 300 patients undergoing constipation treatment during the same period.

(1) Full Analysis Set (FAS) is the set of patients that is as close as possible to the ideal implied by the Intention-to-Treat principle. Specifically, in this trial, the FAS is the data set of all patients with baseline evaluation who take at least one capsule treatment/other treatment option. Missing data for primary efficacy endpoints in the FAS will be imputed according to certain rules while missing data for secondary efficacy endpoints will not be imputed.

(2) Per Protocol Set (PPS) is a subset of the FAS and refers to the set of subjects who meet the inclusion criteria, do not meet the exclusion criteria, complete the treatment, and have no protocol violations. Specifically, in this trial, the PPS includes the patients in the FAS who:

- a) complete the full treatment,
- b) meet the inclusion criteria and do not meet the exclusion criteria,
- c) have good compliance with capsule administration/other treatment, and
- d) have a complete evaluation of the primary efficacy endpoints.

The PPS is a secondary population for efficacy analysis and is used for sensitivity analysis during efficacy analysis.

(3) Safety Data (SS) includes all randomized patients. It is the primary population for safety analysis.

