| Investigational Device | Device Name: Disposable Gastrointestinal Vibrating Capsule (Vibrabot Capsule) Model: ADVC-3 Manufacturer: ANKON Medical Technologies (Shanghai) Co., Ltd. |
| Study Population | Patients with chronic functional constipation |
| Number of Subjects to be Included | 300 |
| Study Design | This study is a multi-center prospective cohort study, which plans to include 300 patients with chronic functional constipation to treat with Vibrabot capsules, and at the same time, include ≥ 300 patients receiving constipation treatment during the same period. During the study, it is necessary to collect the patients' basic |

| | |
|---------------------------------------|--|
| | 
information, baseline constipation status and treatment information, capsule intake during treatment, and concomitant medication. During the treatment phase, patients follow the doctor's advice to receive Vibrabot capsule treatment and maintain stable dietary intake and exercise according to the constipation diagnosis and treatment guidelines.
 
During the study, patients need to scan the QR code or search for the electronic questionnaire "Vibrabot Health" Official Account on WeChat, and fill in the relevant information during the treatment in the electronic questionnaire in a timely and truthful manner. The treatment effect of the patients is evaluated by assessing the number of occurrences of spontaneous bowel movements (SBM) and complete spontaneous bowel movements (CSBM).
 |
| 
Primary Endpoints
 | 
After treatment, whether the response rate of patients using the Vibrabot vibrating capsules alone reaches 50%.
 
The definition of the responder is a patient with an average weekly increase of ≥ 1 complete spontaneous bowel movement (CSBM) compared to the baseline.
 |
| 
Secondary Endpoints
 | 
 1) Proportion of constipated patients who use/do not use other constipation treatment methods during treatment and after the vibrating capsule treatment and at the end of follow-up; 2) Proportion of patients with an average increase of ≥ 1 CSBMs per week compared to the baseline period; 3) Proportion of respondents with an average of ≥ 3 SBMs per week during the treatment period; 4) Proportion of subjects with ≥ 3 SBMs per week and an increase of ≥ 1 CSBMs during at least 4 weeks of treatment compared to baseline; 5) Proportion of patients with an average increase of ≥ 1 CSBMs per |

| | |

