7.2 Effectiveness Evaluation Methods

7.2.1 Primary Efficacy Endpoints

After treatment, whether the response rate of patients using the Vibrabot vibrating capsules alone reaches 50%.

The definition of the responder is a patient with an average weekly increase of ≥ 1 complete spontaneous bowel movement (CSBM) compared to the baseline.

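### Section 8.1 states a null of at most 50% but sizes the trial on a null of 40%, so the claimed 80% power does not belong to the stated hypothesis

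*Combined protocol and SAP*

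**What the plan says.** Section 8.1 (Sample Size Calculation) gives the null as "H0: The effectiveness rate of vibrating capsule treatment for constipation" at or below 50%, with the alternative above 50%. It describes the aim as to "compare it with the expected 50% effectiveness rate, then a one-sample proportion test can be considered for sample size calculation".

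The primary endpoint uses the same benchmark. The Protocol Summary and section 7.2.1 both ask "whether the response rate of patients using the Vibrabot vibrating capsules alone reaches 50" per cent.

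The inputs to the formula, a few lines below the hypotheses, differ:

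- Null rate: "p_0 is the success rate under the null hypothesis (assuming a 40% success rate under the null hypothesis").
- Expected rate: "here it is estimated that the effectiveness of treating constipation with vibrating capsules is 50" per cent.
- Alpha is 0.05 and beta 0.2, which the section translates into 80% power.

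The result is: "At least 191 participants are needed for this study. Assuming a 20% loss to follow-up, the final sample size required is 239". The plan then enrols 300 capsule patients.

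Section 8.2 sets two-sided 0.05 for difference tests. It does not mention the primary endpoint.

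**The concern.** The 40% appears once, as a sample size input, with no justification. The 50% appears in the null, the alternative, the comparison sentence and the endpoint. Nothing reconciles the two.

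Two things are at stake. First, a reader or ethics committee would take the plan to have an 80% chance of showing a rate above 50%, yet the documents assume no true rate above 50% at which that could happen. Second, the success criterion is not fixed. A result near the expected 50% is likely to be positive against 40% and negative against 50%. Section 8.4 allows a change to the statistical plan to be explained in the final report alone, so the choice of null could come after the data are seen.

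**Working it through.** **Inputs from section 8.1.** Sample size null p0 = 0.40; expected rate pT = 0.50; stated null bound 0.50; alpha 0.05; power 0.80; loss 20%; capsule enrolment 300, which leaves 300 × 0.8 = 240 evaluable.

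**Step 1: reproduce the plan's figures.** With the plan's formula and two-sided 0.05 (z = 1.960; z for 80% power = 0.8416):

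n = [1.960·√(0.40·0.60) + 0.8416·√(0.50·0.50)]² / (0.50 − 0.40)² = (0.9602 + 0.4208)² / 0.01 = 190.7, rounded up to 191.

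191 / 0.8 = 238.75, rounded up to 239. Both figures match, so 40% really was the null used. (The printed Z(1−α), read literally as 1.645, gives 150.5, or 151, which does not match.)

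**Step 2: put the stated null into the same formula.** With p0 = 0.50 and pT = 0.50 the denominator is zero, so no finite n exists. The chance of success at a true 50% is then the size of the test: 2.5% in the upper tail of two-sided 0.05, or 5% one-sided. Exact binomial tests give slightly less: 2.1%, 2.3% and 2.2% (two-sided) at n = 191, 240 and 300.

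**Step 3: compare the two nulls at a true rate of 50%.** Power = 1 − Φ([p0 + 1.96·√(p0(1−p0)/n) − p] / √(p(1−p)/n)), two-sided 0.05. The last two columns give the chance that the result beats 40% but not 50%.

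| Evaluable n | Beats 40% | Beats 50% | Beats 40% only, score test (normal) | Beats 40% only, exact tests |
|---|---|---|---|---|
| 191 | 80.1% | 2.5% | 77.6% | 74.4% |
| 240 | 88.1% | 2.5% | 85.6% | 84.1% |
| 300 | 93.9% | 2.5% | 91.4% | 90.4% |

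For n = 240 the score cut-offs are 0.40 + 1.96·√(0.24/240) = 46.20% and 0.50 + 1.96·√(0.25/240) = 56.33%. The null therefore decides the result for 111 to 135 responders (112 to 135 with exact tests).

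**Step 4: what a test against 50% could show.** The documents give no rate above 50%, so the true rates below are assumptions. Two-sided 0.05:

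| True rate | Power, n = 191 | Power, n = 240 | Power, n = 300 | Evaluable n for 80% | Enrolled after 20% loss |
|---|---|---|---|---|---|
| 55% | 28.1% | 34.0% | 40.9% | 783 | 979 |
| 58% | 60.0% | 70.0% | 79.4% | 305 | 382 |
| 60% | 79.4% | 87.7% | 93.8% | 194 | 243 |

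For example, at 60%: [1.960·0.5 + 0.8416·√0.24]² / 0.10² = 193.8, or 194, and 194 / 0.8 = 242.5, or 243. With 240 evaluable, 80% power needs a true rate of about 59%. One-sided 0.05 lowers that to about 58%, and the evaluable numbers at 55%, 58% and 60% become 617, 240 and 153.

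**The case against.** **The endpoint may not call for a test.** It says reaches 50%, section 8.1 names the one-sample test only for sizing, and section 8.2 speaks of difference tests. If success meant an observed rate of at least 50%, its probability at a true 50% would be 50.0%, 52.6% and 52.3% at n = 191, 240 and 300. It is true that no passage ties a test to the endpoint, so the 2.5% or 5% belongs to the test of the printed hypotheses. But the plan gives no observed-rate rule, such a rule would not test the printed alternative, and 80% power would not apply to it either.

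**40% may be the intended null and 50% the target.** Then the hypotheses and the endpoint are wrong. The contradiction remains and only its location changes.

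**The planned 300 may be enough.** This stands in part. The same 10-point margin placed above 50% needs 194 evaluable and 243 enrolled, against the plan's 191 and 239. A test against 50% also still controls type I error. However, 240 is optimistic as a capsule-alone denominator, because section 3.2 allows combination therapy. If 70% of the 240 used capsules alone (an assumption), 168 would remain and power at a true 60% would fall from 88% to 74%.

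**The figures depend on method and sidedness.** They do, since the plan names no method. Exact tests and one-sided levels move the numbers as shown above but leave the conclusion unchanged.

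**Switching nulls needs ethics committee approval.** Section 14 requires this for protocol revisions, which is a safeguard. Because section 8.4 accepts an explanation in the final report alone, the risk is reduced but not removed.

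**Conclusion.** The concern holds, and the plan must be corrected. The arithmetic behind 191 and 239 is right, but those figures and the 80% power describe a test against 40%, while the printed hypotheses and endpoint use 50%. At the plan's own expected rate, the printed test has a success probability of about 2.5% or 5%, depending on sidedness, and no increase in enrolment raises it.

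The practical consequence is large: at a true 50% with 240 evaluable patients, about 84% to 86% of trials would give a result whose sign depends on which null is applied.

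These figures assume a one-sample proportion test at 0.05 and the plan's 20% loss. The fault is the stated power and the unsettled null. It is not shown that 300 patients are too few.

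**What to change.** Before outcome data are reviewed, use one justified null in the hypotheses, the primary endpoint and the sample size calculation. Tie the test to the endpoint, for example: success if the lower limit of the two-sided 95% confidence interval for the capsule-alone response rate, by a method named in advance, exceeds that null.

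- **If the null stays at 50%.** This is the smaller change, since most of the text already uses it. Withdraw the 80% power claim at an expected 50%. Restate power over true rates that the sponsor justifies from evidence, for the expected number of evaluable capsule-alone patients.
- **If the null becomes 40%.** Change the hypotheses and endpoint to 40% and justify it. A test against 50% may follow in a prespecified fixed sequence, only if 40% is rejected, without loss of alpha. No 80% power for exceeding 50% may be claimed at the expected 50%.

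A minor correction, possibly only of notation: print Z(1−α/2) in the formula, since that is what yields 191.

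The cost is a protocol amendment agreed by investigator and sponsor and approved by the ethics committee (section 14), explained as section 8.4 requires, and a less favourable stated power. Restating the power needs no extra patients. More would be needed only if the sponsor wants 80% power against 50% at a true rate below about 59% (two-sided, 240 evaluable capsule-alone patients), or if combination therapy leaves fewer than 240.

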8.2 Statistical Analysis Principle

SAS (version 9.2 or above) or R is used in this study for statistical analysis.

Measurement data are presented as the number of cases, mean±standard deviation, median, minimum, maximum, and quartiles. Count data are presented as frequencies and percentages. Parametric methods are first considered for statistical tests, and non-parametric methods are used if the data distribution differs significantly from the distribution assumed by the statistical test.

A two-sided hypothesis test is used for difference test, and the alpha level is set to 0.05 (two-sided); that is, if the p-value is <0.05, the difference is considered statistically significant.

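### The printed sample-size formula with α = 0.05 gives 151, not the stated 191; 191 needs the two-sided critical value, so Section 8.1 should be aligned with the two-sided 0.05 of Section 8.2.

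*Combined protocol and SAP*

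**What the plan says.** Section 8.1 (Sample Size Calculation) sets a null of at most 50% and a one-directional alternative of more than 50% ("H1: The effectiveness rate of vibrating capsule treatment for constipation" exceeds that value). It prints the normal-approximation formula for a one-sample proportion, whose first term is "Z_{1-\alpha} \sqrt{P_0(1-P_0"), so the critical value carries the subscript 1-α. The inputs listed under the formula are:

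- an expected rate of 50% and a null rate of 40%;
- "The probability of Type I error α is set to 0.05", with no word on one or two sides;
- "the probability of Type II error β is set to 0.2", that is, 80% power.

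The result is "At least 191 participants are needed for this study", raised to 239 for 20% loss to follow-up. The plan then enrols 300 capsule patients.

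Section 8.2 gives the only general testing rule: "A two-sided hypothesis test is used for difference test, and the alpha level is set to 0.05 (two-sided"), with p < 0.05 counted as significant. Neither section states the sidedness or level of the primary one-sample test by name.

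**The concern.** Three features of Section 8.1 point to a one-sided test at 5%: the directional alternative, the subscript 1-α, and an unqualified α of 0.05. The reported N does not come from those inputs. It comes from the critical value of a two-sided 5% test.

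The level of the primary success claim is at stake. An analyst who follows Section 8.1 literally could declare success at a one-sided p below 0.05. One who follows Section 8.2 would need a two-sided p below 0.05, which means at most 2.5% in the favourable direction. The nominal false-positive allowance differs by a factor of two, and so does not give the same number of responders needed for success.

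**Working it through.** **Inputs (all from Section 8.1 unless noted).** P0 = 0.40; PT = 0.50; α = 0.05; β = 0.20; loss 20%; planned enrolment 300. Two-sided 0.05 comes from Section 8.2. Z_β is read as the positive value 0.8416; as a lower-tail quantile it would be negative and the formula would make no sense.

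**Formula.** n = [Zα·√(P0(1-P0)) + Z_β·√(PT(1-PT))]² / (PT-P0)²

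Here √(0.4·0.6) = 0.4899, √(0.5·0.5) = 0.5, and (PT-P0)² = 0.01.

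**Step 1: reproduce the plan's figure.** With Z(1-α/2) = 1.960:
- n = (0.9602 + 0.4208)² / 0.01 = 190.71, so 191.
- 191 / 0.8 = 238.75, so 239.

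Both match the plan exactly.

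**Step 2: use the formula as printed.** With Z(1-α) = 1.645:
- n = (0.8058 + 0.4208)² / 0.01 = 150.46, so 151.
- 151 / 0.8 = 188.75, so 189.

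This is 40 fewer than stated (50 fewer after loss).

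**Step 3: could another method give 191 at one-sided 5%?** None of those tried does:

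| Variant, one-sided 0.05, 80% power | n |
|---|---|
| Null variance only | 149 |
| Alternative variance only | 155 |
| Arcsine | 153 |
| Continuity-corrected | about 153 to 164 |
| Exact binomial | 158 to 164 |

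Changing the power does not help either: the printed formula gives 175.3 at 85% and 209.3 at 90%.

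**Step 4: power against the 40% null (normal approximation).** Power = Φ[(√n·0.1 - Zα·0.4899) / 0.5]

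| n | Two-sided 0.05 | One-sided 0.05 |
|---|---|---|
| 191 | Φ(0.844) = 80.1% | Φ(1.152) = 87.5% |
| 300 | 93.9% | 96.8% |

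**Step 5: success threshold against the stated H0 of 50% (exact binomial).** The smallest responder count whose upper-tail probability at 50% does not exceed the level is:

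| Evaluable | One-sided 0.05 | One-sided 0.025 | Gap |
|---|---|---|---|
| 240 (assumed: 300 × 0.8) | 134 (55.8%), tail 4.1% | 136 (56.7%), tail 2.3% | 2 |
| 300 | 165 (55.0%), tail 4.7% | 168 (56.0%), tail 2.2% | 3 |

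So 134 or 135 of 240, or 165 to 167 of 300, would succeed on one reading and fail on the other. Step 4 uses the 40% null of the calculation and Step 5 the 50% null of the stated hypotheses, so the two tables do not describe a single design.

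**The case against.** The strongest reply is that this is a slip in a subscript. Section 8.2 gives one decision rule, "the alpha level is set to 0.05 (two-sided"), and that rule reproduces 191 and 239 exactly. Comparing a response rate with a fixed 50% can fairly be called a test for a difference, and no other level appears anywhere. The notation in Section 8.1 is loose elsewhere too: the formula uses P_T where the list of terms defines p, and Z_β has to be read as a positive value. A slip is more likely than an undecided error rate.

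Most of this stands. A reader might infer that the plan leaves the type I error of the primary test unset. The documents do not support that: Section 8.2 sets a level and the reported N agrees with it. A reader might also infer that the trial is too small. It is not: 191 reaches 80% power on either reading, and 300 are planned.

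What the reply does not remove is that the formula fails to give its own N, that the hypotheses are directional at an unqualified 0.05, and that the rule in Section 8.2 is never tied to the primary test. Section 8.1 can still be cited for the weaker criterion.

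**Conclusion.** The point holds as an internal error in Section 8.1 with a small effect. The formula is wrong for the N it reports, and a literal reading of the section conflicts with Section 8.2 on the level of the primary test. The best-supported reading is two-sided 0.05 with the wrong subscript printed.

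The nominal favourable-direction level is 5% on one reading and 2.5% on the other, but the affected band of results is only 2 responders in 240 or 3 in 300. There is no sample-size shortfall from this error.

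The thresholds rest on an assumed 240 or 300 evaluable patients. The primary endpoint in Section 7.2.1 covers patients using the capsule alone, and Section 3.2 allows combination therapy, so the evaluable number could be lower.

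A reader might take the exact match as showing that 191 and 239 are sound for the primary test. It shows only which critical value was used. Those figures are for a 40% null, while the stated H0 is at most 50%. If the true rate is the expected 50%, a test of that H0 rejects no more often than its type I error at either level. That conflict is separate and larger.

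**What to change.** In Section 8.1:

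1. Print Z(1-α/2) in the formula.
2. State α as two-sided 0.05, equivalent to one-sided 0.025 in the direction of H1, in line with Section 8.2.
3. State that the primary one-sample test is judged at that level.
4. Describe 191 and 239 only as the output for a 40% null against a 50% expected rate. Reconcile the stated H0 of at most 50% with that calculation before using these numbers to support the primary test.

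Items 1 to 3 cost a line or two of text and no patients, and should be settled before results are seen. Item 4 only labels the figures; resolving the null may change the required N and has to be costed separately.
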